2.2.1 Randomization and drug dispensing irregularities

Randomization and drug-dispensing irregularities occur whenever:

1. A randomization is not in accordance with the protocol-defined randomization method, such as a) an ineligible patient is randomized, b) a patient is randomized based on an incorrect stratum, c) a patient is randomized twice, or d) in a dynamic randomization scheme the treatment assignment is, in fact, not random, due to a computer program error.

OR

2. A patient is dispensed an IMP kit not allocated by the protocol-defined randomization, such as a) a patient at any time in the study is dispensed a different treatment kit than as randomized (which may or may not contain the correct-as-randomized IMP), or b) a nonrandomized patient is treated with IMP reserved for randomized patients.

Randomization and drug-dispensing irregularities will be monitored throughout the study and reviewed on an ongoing basis.

All randomization and drug-dispensing irregularities will be documented in the clinical study report. If the number of irregularities is large enough to make a tabular summary useful, the irregularities will be categorized and summarized among randomized patients (number and percentages). Nonrandomized, treated patients will be described separately. Listings with additional, relevant details will be provided in appendix.

Randomization and drug-dispensing irregularities to be prospectively identified include but are not limited to:

Randomization and drug allocation irregularities

Kit dispensation without IRT transaction

Erroneous kit dispensation

Kit not available

Randomization by error

Patient randomized twice

Stratification error

Patient switched to another site

2.3 ANALYSIS POPULATIONS

Patients treated without being randomized will not be considered randomized and will not be included in any efficacy population.

The randomized population includes any patient who has been allocated to a randomized treatment regardless of whether the treatment kit was used.

For any patient randomized more than once, only the data associated with the first randomization will be used in any analysis population. The safety experience associated with any later randomization will be assessed separately.

The safety experience of patients treated and not randomized will be reported separately, and these patients will not be in the safety population.

2.3.1 Efficacy populations

Efficacy analyses will be based on the treatment group allocated by the IRT according to the randomization schedule at randomization visit (as randomized), irrespective of the treatment actually received.

2.3.1.1 Intent-to-treat population

Efficacy analyses will be based on the ITT population, defined as all randomized patients, irrespective of compliance with the study protocol and procedures. Patients will be analyzed for efficacy according to the treatment group to which they are randomized.

2.3.2 Safety population

Safety analyses will be based on the safety population, defined as all randomized patients who actually receive at least one dose of double-blind IMP (regardless of the amount of treatment administered). Patients will be analyzed according to the treatment actually received.

In addition:

- Nonrandomized but treated patients will not be part of the safety population; however, their safety data will be presented separately.
- Randomized patients for whom it is unclear whether they took the IMP will be included in the safety population as randomized.
- When a patient is exposed to both sotagliflozin and placebo, the patient will be analyzed in the appropriate sotagliflozin group (depending on the treatment kits taken [400 mg or 200 mg]).
- When a patient is exposed to both sotagliflozin 400 mg (treatment kits) and 200 mg (treatment kits), the patient will be analyzed in the sotagliflozin 200 mg group.
- Randomized patients will be excluded from the safety population only if there is documented evidence (ie, all study dates recorded as no medication taken) that patients have not taken the study treatment. If a patient is dispensed double-blind IMP and is lost to follow-up without any documented evidence, the patient will be considered exposed.

2.4 STATISTICAL METHODS

2.4.1 Demographics and baseline characteristics

Continuous data will be summarized using the number of observation available (N), mean, standard deviation (SD), median, minimum, and maximum for each treatment group. Categorical and ordinal data will be summarized using the count and percentage of patients in each treatment group.

Parameters will be summarized on the randomized population analyzed in the treatment group to which they were randomized. Analyses for the safety population will be included in the appendices if the size of the safety population is different (>10%) from the size of that in the primary analysis population for any treatment group.

Parameters described in [Section 2.1.1](#) will be summarized by treatment group and overall treatment groups using descriptive statistics.

Medical/surgical history will be classified into primary system organ class (SOCs) and HLTs using MedDRA and will be summarized by treatment groups. Events will be sorted by SOC internationally agreed order and decreasing frequency of HLT based on incidence in the overall treatment group.

P-values on the treatment difference for the demographic and baseline characteristic data will not be calculated.

In general, no specific description of the safety parameters will be provided at Baseline. If relevant, the baseline values will be described along with each safety analysis.

In general, no specific description of the efficacy parameters will be provided at Baseline. If relevant, the baseline values will be described along with each efficacy analysis.

2.4.2 Prior or concomitant medications

The prior, concomitant and posttreatment medications will be presented in the randomized population for each treatment group (and overall for the summary of prior medications), using counts and percentages. No statistical test for the between-group difference will be performed.

Medications will be summarized by treatment group according to the WHO-DD dictionary, considering the first digit of the anatomic therapeutic category (ATC) class (anatomic category) and the first 3 digits of the ATC class (therapeutic category). A given medication may be classified in more than 1 ATC class. All ATC codes corresponding to a medication will be summarized, and patients will be counted once in each ATC category (anatomic or therapeutic) linked to the medication. Therefore patients may be counted several times for the same medication.

Prior medications will be presented by anatomic and therapeutic categories and sorted by decreasing frequency of ATC based on the overall incidence across treatment groups. In case of equal frequency regarding ATCs (anatomic or therapeutic categories), alphabetical order will be used.

Concomitant and posttreatment medications will be presented by anatomic and therapeutic categories and sorted by decreasing frequency of ATC based on the incidence in the sotagliflozin 400 mg group. In case of equal frequency regarding ATCs (anatomic or therapeutic categories), alphabetical order will be used.

Antidiabetic medications will be presented separately by pharmacological class, chemical class and standardized medication name.

2.4.3 Extent of investigational medicinal product exposure and compliance

The extent of IMP exposure and compliance will be assessed and summarized by actual treatment within the safety population ([Section 2.3.2](#)).

2.4.3.1 Extent of investigational medicinal product exposure

The extent of IMP exposure will be assessed by the duration of IMP exposure.

Duration of IMP exposure is defined as last dose date of double-blind IMP – first dose date of double-blind IMP + 1 day, regardless of unplanned intermittent discontinuations (see [Section 2.5.3](#) for calculation in case of missing or incomplete data).

Duration of IMP exposure will be summarized descriptively as a quantitative variable (number of patients exposed, mean, SD, median, minimum, and maximum) during the 26-week core treatment period and 104-week entire treatment period, respectively. In addition, duration of treatment exposure will also be summarized categorically by numbers and percentages for each of the following categories and cumulatively according to these categories:

- 1 to 28 days.
- 29 to 56 days.
- 57 to 84 days.
- 85 to 126 days.
- 127 to 182 days.
- 183 to 364 days.
- 365 to 551 days.
- 552 to 728 days.
- >728 days.

Additionally, the cumulative duration of treatment exposure will be provided, defined as the sum of the duration of treatment exposure for all patients, and will be expressed in patient years.

Number and percentage of patients by final dose at the end of the treatment will also be presented by each treatment group.

2.4.3.2 Compliance

A given administration will be considered noncompliant if the patient did not take the planned dose of treatment as required by the protocol. No imputation will be made for patients with missing or incomplete data.

Percentage of compliance for a patient will be defined as the number of days that the patient was compliant divided by the total number of days that the patient was planned to take double-blind IMP during the treatment epoch defined in [Section 2.1.4](#) (ie, from the first date to the last date of double-blind IMP administration).

Above-planned dosing percentage for a patient will be defined as the number of days that the patient took a higher dose than planned divided by the total number of days that the patient was planned to take double-blind IMP during the treatment epoch.

Under-planned dosing percentage for a patient will be defined as the number of days that the patient took a lower dose than planned divided by the total number of days that the patient was planned to take double-blind IMP during the treatment epoch.

Treatment compliance, above-planned, and under-planned dosing percentages will be summarized descriptively as quantitative variables (number, mean, SD, median, minimum, and maximum). The percentage of patients whose compliance is <80% will be summarized. In addition, numbers and percentages of patients with at least 1 day above-planned dose will also be provided, as well as numbers and percentages of patients with 0, (0, 20%], and >20% of days under-planned dose administrations.

Cases of overdose (see study protocol for further details) will constitute AEs/SAEs and will be listed as such. More generally, dosing irregularities will be listed in [Section 2.2.1](#).

2.4.4 Analyses of efficacy endpoints

Efficacy analyses will be performed on the ITT population using the efficacy assessments collected during the study, including those obtained after IMP discontinuation or introduction of rescue therapy (de facto estimand), unless otherwise specified.

Statistical testing will be performed for primary endpoint and secondary endpoints at Week 26 (or Week 12 for SBP). The superiority tests will be two-sided tests at nominal 5% significance level. All efficacy endpoints, other than primary and main secondary efficacy endpoints, will only be summarized by descriptive statistics without formal statistical testing.

Missing data for efficacy analyses is identified through steps described in [Section 2.5.4](#).

2.4.4.1 Analysis of primary efficacy endpoint(s)

Primary analysis

The primary efficacy endpoint of change in HbA1c from Baseline to Week 26 will be analyzed by an Analysis of Covariance (ANCOVA) model using HbA1c values measured at Baseline and Week 26 (observed or imputed). The missing data at endpoint will be imputed by multiple imputation (MI) methods as detailed below. To be concise, the following texts related to imputation are generalized to accommodate primary as well as continuous secondary efficacy endpoints.

Missing endpoint data at Week 26 (or Week 12 for SBP) visit will be imputed using a model built separately in each treatment group and estimated from the patients in the same treatment group who prematurely discontinue the IMP before the Week 26 (or Week 12 for SBP) visit but have the measurement for the endpoint (ie, retrieved dropouts). The imputation model will include the randomization strata and the corresponding baseline value. In cases of non-convergence during the imputations, the offending stratum will be identified and then will be dropped from the model. Considering that the number of retrieved dropout patients in each treatment group is expected to be small, a simple imputation model based on regression will be used with baseline measurement included as the predictor. This will serve as the primary method of imputation for missing data should sampling criteria be satisfied (see below).

An alternative (back-up) imputation method will be used if the number of patients who prematurely discontinue the IMP before the Week 26 (or Week 12 for SBP) visit but have the measurement for the endpoint is < 5 in any treatment groups (ie, an insufficient number of retrieved dropouts to support the imputation method described above). This criterion will be assessed for each primary or continuous secondary efficacy endpoint.

In the back-up imputation method, missing post-Baseline endpoint values at Week 26 (or Week 12 for SBP) will be imputed by the washout Multiple Imputation (MI) method under the missing not at random (MNAR) framework.

Missing endpoint data at the Week 26 (or Week 12 for SBP) in all treatment groups (sotagliflozin 400 mg, sotagliflozin 200 mg and placebo) are imputed from a model estimated from patients in the placebo group who have the endpoint data available.

For patients in the sotagliflozin groups with missing data at Week 26 (or Week 12 for SBP), their missing values will be imputed using observed baseline and the observed primary endpoint data from placebo completers; no intermittent values from either placebo or the active treatment groups will be used.

For placebo patients, missing data will be imputed based on the placebo group data. Intermittent observed values will be used while imputing missing values at Week 26 (or Week 12 for SBP). In cases that a non-monotone missing data pattern occurs at the intermediate visits, these data points will be first imputed in the placebo group using the Markov Chain Monte Carlo (MCMC) option in PROC MI to achieve a monotone missing pattern for all placebo patients. The Week 26 (or Week 12 for SBP) endpoint values will be subsequently imputed from the multiple copies of the original dataset where each copy will have a monotone missing pattern.

The imputation models for the washout MI method will include the randomization strata and the corresponding baseline value. Missing data will be imputed using the regression method. In cases of non-convergence during the imputations, especially for the MCMC application in the placebo non-monotone datasets, graphical measures (eg, trace and autocorrelation plots) will be used to identify the offending variable and once detected, that variable(s) will be dropped from the model and the imputations will be re-run. These re-run models will use the same seed number and number of imputations as used in the original models.

Using either imputation method, missing endpoint data will be imputed 2000 times to generate multiple data sets with complete data. Other details of the imputation procedures such as the seed number and sort ordering are specified in the SAS programs. The HbA1c change from Baseline to Week 26 will be derived from observed and imputed HbA1c values at Week 26.

Each of the completed datasets after the imputation will be analyzed using the Analysis of Covariance (ANCOVA) model with treatment groups (sotagliflozin 400 mg, sotagliflozin 200 mg, placebo), randomization stratum of HbA1c ($\leq 8.5\%$, $> 8.5\%$), randomization stratum of sex (male, female), and country as fixed factors, and baseline value of the efficacy endpoint as a covariate.

Results from each analysis will be combined using Rubin's formula, to provide the adjusted mean change in HbA1c from Baseline to Week 26 (or Week 12 for SBP) for each treatment group, as well as the between-group difference (comparing sotagliflozin 400 mg or sotagliflozin 200mg, respectively, versus placebo) and its associated 95% confidence interval (CI).

Sensitivity analyses

Tipping point analysis based on the same MI method as applied to primary analysis will be performed to examine the robustness of the results from the primary analysis. Patients who were randomized to sotagliflozin 400 mg group and had no HbA1c data at Week 26 will be given a penalty. The penalty will be gradually increased to evaluate at which level the conclusion of the analyses in terms of statistical significance is changed. The tipping point is the penalty level, at which the magnitude of efficacy reduction in patients without HbA1c data at Week 26 creates a shift in the treatment effect of sotagliflozin 400 mg from being statistically significantly better than placebo to a non-statistically significant effect. LS mean difference between sotagliflozin 400 mg and placebo and its associated p-value will be provided for each penalty level. The steps to perform the tipping point analysis comparing sotagliflozin 400 mg versus placebo are as follows:

1. Missing data will be imputed using same MI method as applied for primary analysis,
2. The imputed HbA1c value at Week 26 in the sotagliflozin 400 mg group will be penalized by adding a penalty δ (eg, $\delta = 0.1\%$) in each complete dataset,
3. Change from Baseline at Week 26 in HbA1c will be analyzed using the same ANCOVA model as specified in the primary analysis in each complete dataset,
4. Results will be combined across complete datasets using Rubin's rule,
5. Steps 2 to 4 will be repeated with incremental penalty at δ (ie, δ , 2δ , 3δ ...) until the p-value for treatment effect of sotagliflozin 400 mg compared to placebo estimated in Step 4 is > 0.05 .

The above tipping point analysis will be replicated to examine the robustness of the treatment effect of sotagliflozin 200 mg (ie, adding penalty to the sotagliflozin 200 mg group instead of sotagliflozin 400 mg group in Step 2).

The tipping point analysis will be performed on the ITT population. The tipping point analyses will be performed only if the corresponding primary or secondary endpoints (change from Baseline to Week 26 in HbA1c comparing sotagliflozin 400 mg vs placebo, or comparing sotagliflozin 200 mg vs placebo) is statistically significant at $\alpha = 0.05$ (2-sided).

In addition to the tipping point analyses, if the retrieved dropout imputation is applied to the primary analysis, the analysis based on the washout imputation method (ie, the backup imputation method) will be presented as a sensitivity analysis.

Assessment of treatment effect by subgroup

Descriptive analyses will be performed on the primary endpoint to summarize the treatment effects across subgroups defined by the following Baseline or Screening factors:

- Race (White, Black or African American, Asian, Other) (any race groups with fewer than 5 patients may be combined with “Other” category as appropriate).
- Ethnicity (Hispanic, Not Hispanic).
- Age group (<65, ≥ 65 years),
- Gender (Male, Female).
- Baseline BMI level (<30, ≥ 30 kg/m²).
- Baseline HbA1c ($\leq 8.5\%$, $> 8.5\%$).
- Baseline mean SBP (<130 mmHg, ≥ 130 mmHg).
- Baseline eGFR (≥ 30 to <60 mL/min/1.73m² [Moderate decrease in GFR], ≥ 60 to <90 mL/min/1.73m² [Mild decrease in GFR], and ≥ 90 mL/min/1.73m² [Normal]).
- Duration of diabetes (<10, ≥ 10 years).
- Prior antidiabetic medication [No antidiabetic therapy, Insulin (alone or with other antihyperglycemic agents), SU and/or glinide (alone or with other non-insulin antihyperglycemic agents), other (non-insulin antihyperglycemic agents except SU, and glinide)].
- Country.

The treatment effects (sotagliflozin 400 mg and sotagliflozin 200mg, respectively, versus placebo) across the subgroups defined for each of these factors will be estimated for the change from Baseline to Week 26 in HbA1c in the ITT population, and using the same MI method as applied to the primary analysis.

The ANCOVA model will include treatment groups (sotagliflozin 400 mg, sotagliflozin 200 mg, placebo), randomization stratum of HbA1c ($\leq 8.5\%$, $> 8.5\%$), randomization stratum of sex

(male, female), subgroup factor, treatment-by-subgroup factor, and country as fixed factors and using baseline HbA1c value as a covariate. The adjusted estimates of treatment mean differences (sotagliflozin 400 mg versus placebo and sotagliflozin 200 mg versus placebo) with SE and 95% CIs will be provided as appropriate across the subgroups. A forest plot of the results will also be presented.

In the case that the subgroup factor is identical or similar to a randomization strata factor (eg, baseline HbA1c category or sex), only the subgroup factor (as a single factor and/or an interaction term) will be included in the model in order to avoid the issue of collinearity in the analysis. The corresponding strata factor will not be included in the model.

Summary statistics at scheduled visits

Summary statistics (for screening value, baseline value, observed post-Baseline value and its changes from Baseline) at scheduled visits will be provided for each treatment group. The summary will include the number of observations, mean, SD, SE, minimum, median, and maximum. Graphical presentations will also be used to examine trends over time using mean values (\pm SE) and mean changes from Baseline (\pm SE) at each of the scheduled visits.

Similar presentations will be provided excluding measurements after rescue therapy during the entire 104-week double-blind treatment period.

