2.4.4.2 Analyses of secondary efficacy endpoints

For continuous secondary efficacy endpoints (see Section 2.1.3) with missing data at Baseline, missing data will be imputed using MI under the assumption of missing at random (MAR). Missing data at Baseline will be imputed using regression method that includes randomization stratum of HbA1c ($\leq 8.5\%$, $> 8.5\%$), randomization stratum of sex (male, female) and baseline value in the imputation model.

Each continuous secondary efficacy endpoint (Section 2.1.3) will be analyzed using a similar ANCOVA model including the measurements at Baseline and endpoint (observed or imputed). The missing data at endpoint will be imputed by the retrieved dropouts if there are at least 5 patients in each study treatment group who discontinued but have the endpoint. Otherwise, the washout imputation method will be used. After the imputation, each of the complete datasets will be analyzed by an ANCOVA model with treatment groups (sotagliflozin 400 mg, sotagliflozin 200 mg, placebo), randomization stratum of HbA1c ($\leq 8.5\%$, $> 8.5\%$), randomization stratum of sex (male, female), and country as fixed effects, and baseline secondary endpoint value as a covariate.

Results from each complete dataset will be combined using Rubin's rule to provide the adjusted mean change from Baseline to week 26 (or week 12 for SBP) for each treatment group, as well as the between treatment group difference (comparing each sotagliflozin group to placebo group) and the 95% CI for the between-group difference.

For all continuous secondary endpoints, summary statistics at scheduled visits will be provided for each treatment group. The summary will include the number of observations, mean, SD, SE,

minimum, median, and maximum. Graphical presentations will also be used to examine trends over time using mean (\pm SE) and mean change from Baseline (\pm SE) at each of the scheduled visits. In addition, SBP will be summarized descriptively at each visit for those with baseline SBP \geq 140 mmHg.

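### The retrieved-dropout imputation model is described both with and without the randomization strata, and the strata version is unusable at the minimum of five patients per arm; the BMD back-up method also differs between SAP 2.4.5.1 and Appendix C

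*SAP*

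**What the plan says.** SAP 2.4.4.1 states that missing endpoint data "will be imputed using a model built separately in each treatment group and estimated from the patients in the same treatment group". The patients meant are early stoppers whose endpoint was nevertheless measured. The same paragraph then describes the model twice:

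- First description: "The imputation model will include the randomization strata and the corresponding baseline value". It comes with a rule for removing a stratum, which reads "In cases of non-convergence during the imputations, the offending stratum will be identified and then will be dropped from the model".
- Second description: the reason offered is "Considering that the number of retrieved dropout patients in each treatment group is expected to be small", and the model then named is "a simple imputation model based on regression will be used with baseline measurement included as the predictor".

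The method is primary unless a count condition fails. The condition for switching to washout imputation reads, in part, "measurement for the endpoint is < 5 in any treatment groups (ie, an insufficient number of retrieved dropouts to support the imputation method". SAP 2.4.4.2 repeats the threshold for the continuous secondary endpoints: "imputed by the retrieved dropouts if there are at least 5 patients in each study treatment group who discontinued but have the endpoint". On the role of washout when the retrieved-dropout method is primary, the SAP says "the analysis based on the washout imputation method (ie, the backup imputation method) will be presented as a sensitivity analysis".

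SAP 2.4.5.1 repeats both model descriptions, the non-convergence rule and the minimum of five for BMD. Its back-up is the pattern-based multiple imputation set out in that section. Appendix C gives a different back-up: LOCF for BMD at Week 26, and MMRM at Weeks 52 and 104.

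**The concern.** The HbA1c analysis opens the testing hierarchy in SAP 2.4.4.4, so its imputation model should not have to be inferred. Two programmers could follow this paragraph, one keeping the strata and one using baseline only, and get very different standard errors for the same data. The difference is largest at the smallest count for which the method is primary. The only stated safeguard is a convergence rule, and a least-squares fit does not normally trigger one. What is at stake is power and interval width for the primary test. For BMD, the question is also which estimate counts as primary when few retrieved dropouts are available.

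**Working it through.** **1. The plan's own figure.** Inputs from SAP 1.3: SD 1.2, difference 0.6, 120 per arm, two-sided 0.05. The standard error is 1.2 × √(2/120) = 0.155. The ratio is 0.6/0.155 = 3.87, and a noncentral t with 238 df gives 97.1%. The stated 97% is reproduced with no missing values.

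**2. Residual degrees of freedom at five patients.**
- Strata version: intercept, baseline, HbA1c stratum and sex are 4 coefficients, so 5 − 4 = 1 (0 if the two strata are crossed).
- Baseline only: 2 coefficients, so 5 − 2 = 3.

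**3. What that does to the imputations.** Regression imputation draws a residual variance as s² × ν/χ²(ν).
- With ν = 1 the draw has no finite mean. Its 95th percentile is s²/0.00393, about 254 s². The drawn SD exceeds 5s with probability P(χ²₁ < 1/25) = 16%. The planned 2000 imputations would not stabilise this.
- With ν = 3 the mean draw is 3/(3 − 2) = 3 times s²: imprecise, but usable.

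**4. Does the non-convergence rule help?** Least squares is closed-form, so a full-rank fit with 1 df returns an answer. The rule could act only on a rank-deficient design. If 40% to 20% of patients have screening HbA1c above 8.5%, sex is 50:50 and strata are independent of baseline (all assumed), that happens in 20% to 41% of arms of five. In the other 59% to 80% the rule has nothing to act on.

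**5. Power at fixed counts.** The documents give no HbA1c missing or retrieval rate, so the counts are assumptions. Other assumptions: 120 per arm, the −0.6 effect retained after stopping, baseline SD 0.9, country omitted. Each completed data set was analysed by ANCOVA with treatment, strata and baseline, and combined by Rubin's rule. A stratum was dropped only when the design was rank-deficient. Ranges cover simulations with slightly different settings; Monte Carlo error is up to about 2 points.

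| Retrieved / missing per arm | Strata + baseline | Baseline only | Washout |
|---|---|---|---|
| 5 / 2 | 5-17% | 95-98% | 97% |
| 5 / 8 | 2-5% | 79-85% | 95% |
| 5 / 12 | <1-5% | 68-75% | 93-95% |
| 8 / 12 | 79-80% | 90-91% | – |
| 10 / 12 | 88% | 91-93% | – |

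By ten retrieved per arm the two models nearly agree.

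**6. How typical are those cells?** Take discontinuation of 10, 15 or 20% and retrieval of 40, 60 or 75%, giving nine combinations. For each, p = discontinuation × retrieval, X is binomial(120, p), and there are three independent arms.
- P(smallest arm has 5 to 7) = P(X ≥ 5)³ − P(X ≥ 8)³. At 15% and 60%, p = 0.09 and this is 0.959 − 0.627 = 33%. Over the nine combinations it runs from 0.5% to 54%.
- All three arms at exactly five: at most 0.6% of trials. Both arms of the primary comparison at five: at most 3.2%.

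**7. Overall power of the rule as written**, with washout whenever any arm is below five:

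| Assumption | Strata | Baseline only | Washout throughout |
|---|---|---|---|
| Effect retained after stopping (9 combinations) | 69-96% | 89-97% | 93-98% |
| No effect after stopping (4 combinations) | 52-80% | 69-92% | 85-94% |

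**8. BMD back-up, side by side.**

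| Source | Week 26 | Weeks 52 and 104 |
|---|---|---|
| SAP 2.4.5.1 | pattern-based MI | pattern-based MI |
| SAP Appendix C | LOCF | MMRM |
| Protocol 11.4.3.1 (main method) | LOCF | MMRM |

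Appendix C appears to keep the protocol's methods after the SAP text moved to multiple imputation.

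**The case against.** The best reply is that the paragraph already answers the question. The strata sentence is followed by a reasoned narrowing to baseline only, and the next sentence, which makes this the primary method, most naturally refers to that simpler model. On this reading the overall loss is modest: 89-97% against 93-98% for washout when the effect persists. Cells with every arm at five are rare. Washout results are reported in any case, and a significant result is followed by a tipping-point analysis. For BMD no significance test is planned, and pattern-based imputation is reported alongside.

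Most of this stands. Baseline only is the likely intent, and the fixed-count results should not be the headline. It does not remove the point. A rule for dropping a stratum makes sense only if strata are in the model, and nothing marks the first description as superseded. A sensitivity analysis also cannot stand in for the test that opens the hierarchy.

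A reader might infer more than the documents support:
- **That counts near five are what the sponsor expects.** The SAP says only that they will be small. Protocol 6.2.2 presses for return visits, especially at Week 26, which favours higher counts.
- **That the minimum of five is an error.** No document supports another number. At an assumed 15% discontinuation and 60% retrieval, the SAP's chosen method would be primary in 96% of trials with a minimum of 5, 63% with 8 and 27% with 10. Below the minimum, washout borrows from placebo, which is a different assumption.
- **That the analysis is biased or inflates type I error.** The calculations show lost power and wide intervals only.

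**Conclusion.** The point holds as an ambiguity in the primary imputation model with one unusable branch. At five retrieved dropouts per arm the strata version has 1 residual df, the non-convergence rule does not reliably remove the strata, and the primary test would have little power. On the likely baseline-only reading the cost is modest unless many values are missing or the effect is lost after stopping. The power ranges rest on assumed discontinuation, retrieval and missing counts, because the documents give none for HbA1c. The degrees-of-freedom argument and the conflict over the BMD back-up need no such assumptions: SAP 2.4.5.1 and Appendix C name different methods for the key secondary safety endpoint at Week 26 and for BMD at the later time points.

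**What to change.** 1. In SAP 2.4.4.1 and 2.4.5.1, delete the strata sentence and its non-convergence rule from the retrieved-dropout model, so that baseline is the only predictor. The separate washout model in 2.4.4.1 is not affected.
2. In Appendix C, name the pattern-based multiple imputation of 2.4.5.1 as the BMD back-up at Weeks 26, 52 and 104, in place of LOCF and MMRM. The supportive-analysis column carries the same two entries and should be checked at the same time.

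Both are short text changes, with at most a small program change, and should be made before unblinding. Neither has a real statistical cost.

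Optional, for the sponsor to weigh and not a required correction: a prespecified minimum above five per arm. With baseline only and a minimum of 8 or 10, overall power was 93-98% over the nine combinations with the effect retained. The price is that washout imputation becomes primary more often.
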